3.2 END OF STUDY AND LENGTH OF STUDY

The end of this study is defined as the date when the last patient, last visit occurs. The end of the study is expected to occur approximately 6 months after the last patient is enrolled.

The total length of the study, from screening of the first patient to the end of the study, is expected to be approximately 17 months.

In addition, the Sponsor may decide to terminate the study at any time.

3.3 RATIONALE FOR STUDY DESIGN

3.3.2 Rationale for Patient Population

See Section 1 for details on the high unmet medical need for new therapies for patients with moderate to severe AD.

3.3.3 Rationale for Control Group

A placebo-treated control group will be used in this study to assess differences in efficacy and safety in patients who receive MSTT1041A compared with patients who receive placebo. The use of a control group is necessary given the inherent variability in self-reported symptoms and investigator assessments. All patients will continue to receive standard-of-care treatment in addition to study drug (MSTT1041A or placebo) throughout the study.

3.3.4 Rationale for Biomarker Assessments

Biomarker assessments, before and at various timepoints after treatment, will be used to provide evidence of the biologic activity of MSTT1041A in patients, identify biomarkers that may be predictive of response to MSTT1041A, define PK and/or pharmacodynamic (PD) relationships, advance the understanding of the mechanism of action of MSTT1041A in patients, support selection of a recommended dose regimen, and increase the knowledge and understanding of disease biology.

4. MATERIALS AND METHODS

4.1 PATIENTS

Approximately 90 patients with moderate to severe AD will be enrolled in this study.

4.1.1 Inclusion Criteria

Patients must meet the following criteria for study entry:

- Signed Informed Consent Form
- Age 18–75 years at time of signing Informed Consent Form
- Body mass index of 18–40 kg/m² and weight \geq 40 kg at screening
- Ability to comply with the study protocol, in the investigator's judgment

- Ability to understand and complete study-related questionnaires
- Chronic AD, (according to American Academy of Dermatology Consensus Criteria [Eichenfield et al. 2014]), that has been present for at least 3 years before the screening visit
- EASI score ≥ 16 at screening and the randomization (Day 1) visit
- IGA score ≥ 3 (on the 0 to 4 IGA scale, in which 3 is moderate and 4 is severe) at screening and the randomization (Day 1) visit
- $\geq 10\%$ BSA of AD involvement at screening and the randomization (Day 1) visit
- Pruritus NRS score for maximum itch intensity ≥ 3 at screening and the randomization (Day 1) visit
- Documented recent history (within 6 months before the screening visit) of inadequate response to treatment with topical medications or for whom topical treatments are otherwise medically inadvisable (e.g., because of important side effects or safety risks)

Inadequate response is defined as failure to achieve and maintain remission or a low disease activity state (comparable to IGA 0=clear to 2=mild) despite treatment with a daily regimen of TCS of medium to higher potency (\pm TCI as appropriate), applied for at least 4 weeks or for the maximum duration recommended by the product prescribing information (e.g., 2 weeks for ultra-high potent TCS; see [Appendix 2](#)), whichever is shorter.

Patients with documented systemic treatment (e.g., oral, IV) for AD at any point during the past 6 months are also considered as inadequate responders to topical treatments and are potentially eligible for the study after appropriate washout.

Important side effects or safety risks are those that outweigh the potential treatment benefits and include intolerance to treatment, hypersensitivity reactions, significant skin atrophy, and systemic effects, as assessed by the investigator or by the patient's treating physician.

Acceptable documentation includes contemporaneous chart notes that record topical medication prescription and treatment outcome, or investigator documentation based on communication with the patient's treating physician. If documentation is inadequate, potential patients may be re-screened after such documentation is obtained (e.g., patients are shown to fail a 4-week course of mid-to-higher potency TCS [\pm TCI]; see [Appendix 2](#) for examples of TCS classified by potency).

- Have applied a stable dose of topical emollient (moisturizer) twice daily for at least the 7 consecutive days immediately before the randomization visit (see Section [4.1.2](#) for limitations regarding emollients).

- For women of childbearing potential: agreement to remain abstinent (refrain from heterosexual intercourse) or use contraceptive method and agreement to refrain from donating eggs, as defined below:
 - Women must remain abstinent or use contraceptive methods with a failure rate of < 1% per year during the treatment period and for 12 weeks after the final dose of study drug.

A woman is considered to be of childbearing potential if she is postmenarcheal, has not reached a postmenopausal state (≥ 12 continuous months of amenorrhea with no identified cause other than menopause), and has not undergone surgical sterilization (removal of ovaries and/or uterus). The definition of childbearing potential may be adapted for alignment with local guidelines or requirements.

Examples of contraceptive methods with a failure rate of < 1% per year include bilateral tubal ligation, male sterilization, hormonal contraceptives that inhibit ovulation, hormone-releasing intrauterine devices, and copper intrauterine devices.

The reliability of sexual abstinence should be evaluated in relation to the duration of the clinical trial and the preferred and usual lifestyle of the patient. Periodic abstinence (e.g., calendar, ovulation, symptothermal, or postovulation methods) and withdrawal are not acceptable methods of contraception.
- For men: agreement to remain abstinent (refrain from heterosexual intercourse) or use a condom, and agreement to refrain from donating sperm, as defined below:
 - With a female partner of childbearing potential or pregnant female partner, men must remain abstinent or use a condom during the treatment period and for at least 12 weeks after the final dose of study drug to avoid exposing the embryo. Men must refrain from donating sperm during this same period.

The reliability of sexual abstinence should be evaluated in relation to the duration of the clinical trial and the preferred and usual lifestyle of the patient. Periodic abstinence (e.g., calendar, ovulation, symptothermal, or postovulation methods) and withdrawal are not acceptable methods of preventing drug exposure.

4.1.2 Exclusion Criteria

Patients who meet any of the following criteria will be excluded from study entry:

- Pregnant or breastfeeding, or intending to become pregnant during the study or within 12 weeks after the final dose of study drug

Women of childbearing potential must have a negative serum pregnancy test result during the screening period and a negative urine pregnancy test at the randomization visit

- Prior treatment with MSTT1041A

- Use of any of the following:

Treatment with any investigational therapy (with the exception of biologics) within 8 weeks or within 5 half-lives (if known), whichever is longer, before screening

Treatment with immunomodulatory, immunosuppressive (e.g., systemic corticosteroids, methotrexate, mycophenolate-mofetil, IFN- γ , Janus kinase inhibitors, cyclosporine, azathioprine, etc.) within 4 weeks before screening or any condition (e.g., severe asthma) that, in the opinion of the investigator, is likely to require such treatment during the course of the study

Treatment with investigational or licensed biologics as follows:

- Any cell-depleting agents including but not limited to rituximab: within 6 months before screening, or until lymphocyte count returns to normal, whichever is longer
- Other biologics: within 3 months or 5 half-lives (if known) before screening, whichever is longer

- Use of any of the following treatments within 2 weeks before screening, or any condition that, in the opinion of the investigator, is likely to require such treatment during the course of the study:

Regular use (more than 2 visits per week) of a tanning booth/parlor

Phototherapy

- Treatment with TCS or TCIs within 1 week before the randomization (Day 1) visit
- Initiation of treatment for AD with prescription moisturizers or moisturizers containing additives such as ceramide, hyaluronic acid, urea, or filaggrin degradation products within 1 week before the randomization (Day 1) visit
- Initiation of or change in allergen immunotherapy within 12 weeks before screening
- Use of any of the following treatments within 4 weeks before screening, or any condition that, in the opinion of the investigator, is likely to require such treatment during the course of the study:

Treatment with immunoglobulin or blood products

Treatment with any live, attenuated vaccine

- Acute or chronic infection requiring either surgical intervention (e.g., drainage) or medical therapy (e.g., antibiotics, antiviral, antiparasitics, antifungal, or antiprotozoals) within 2 weeks before screening or superficial skin infections within 1 week before the randomization visit.

Note: Patients may be rescreened after infection resolves.

- Positive test for TB during screening, defined as either a positive purified protein derivative (PPD) (≥ 5 mm of induration 48–72 hours after injection) or a positive QuantiFERON TB-Gold® (QFT) test

Patients with a history of Bacille Calmette-Guérin vaccination should be screened using the QFT only; the following criteria for the QFT apply:

An indeterminate QFT should be repeated

A positive QFT or two successive indeterminate QFT results should be considered a positive diagnostic TB test

An indeterminate QFT followed by a negative QFT test, should be considered a negative diagnostic TB test

Patients with a positive PPD test (without a history of Bacillus Calmette-Guérin vaccination) or patients with a positive QFT (see criteria above) are eligible if they meet all of the following criteria:

No symptoms consistent with TB (see TB worksheet provided by Genentech)

Documented history of a completed course of adequate prophylaxis (completed treatment for latent TB per the treatment options as stated in the WHO guideline) before screening

No known exposure to a case of active TB after most recent prophylaxis

No evidence of active TB on chest X-ray within 3 months before screening

- History of any known immunodeficiency disorder, including but not limited to HIV infection
- Positive hepatitis C virus (HCV) antibody test result at screening
- Ineligible test results for hepatitis B surface antigen (HBsAg), hepatitis B surface antibody (HBsAb), and hepatitis B core antibody (HBcAb) total at screening as defined below (see also Flowchart in [Appendix 3](#)):

If HBsAg testing is positive, patient is not eligible. For patients with a negative HBsAg testing, following criteria apply:

If HBsAb testing is negative and HBcAb is positive, patient is not eligible.

If HBsAb testing is positive and HBcAb is negative, patient is eligible.

If HBsAb testing is negative and HBcAb is negative, patient is eligible.

If HBsAb testing is positive and HBcAb is positive, patient must undergo further testing for hepatitis B virus (HBV) DNA:

- Patient is not eligible, if HBV DNA test value is ≥ 20 IU/mL or test cannot be performed.
- Patient is eligible, if HBV DNA test value is < 20 IU/mL.
- Evidence of active liver disease, including jaundice or AST, ALT, total bilirubin, or ALP $> 2 \times$ upper limit of normal (ULN) at screening

- History of anaphylaxis, hypersensitivity to a biologic agent, or known hypersensitivity to any component of the MSTT1041A or placebo injection
- Neutrophil count $\leq 0.5 \times 10^3/\mu\text{L}$ at screening
- Platelet count $\leq 50 \times 10^3/\mu\text{L}$ at screening
- Presence of skin comorbidities that may interfere with study assessments, in the opinion of the investigator
- Active malignancy, including cutaneous basal or squamous cell carcinoma or melanoma
- History of malignancy within 5 years before screening, except for cases of cervical carcinoma in situ or breast ductal carcinoma in situ that have been treated and considered cured
- Helminthic parasitic infection diagnosed within 6 months before screening that has not been treated or has not responded to standard-of-care therapy or exposure to water-born parasites within 6 weeks before screening
- History or evidence of substance abuse that would pose a risk to patient safety, interfere with the conduct of the study, have an impact on the study results, or affect the patient's ability to participate in the study, in the opinion of the investigator
- Hemoglobin A1c (HbA_{1c}) $> 8.5\%$ at screening or any other clinically significant finding that, in the opinion of the investigator, may define uncontrolled diabetes
- History of myocardial infarction, congestive heart failure NYHA Class III and IV, unstable angina pectoris, or stroke within 12 months before screening
- History or presence of complete left bundle branch block, second- or third-degree atrioventricular heart block, or evidence of prior myocardial infarction on ECG, or any abnormality that is clinically significant in the investigator's opinion
- QT interval corrected through use of Fridericia's formula (QTcF) > 450 ms, if patient is male, or QTcF > 470 ms, if patient is female
- History of ventricular dysrhythmias or risk factors for ventricular dysrhythmias such as diagnosed structural heart disease (e.g., left ventricular systolic dysfunction, left ventricular hypertrophy), coronary heart disease, clinically significant electrolyte abnormalities (e.g., hypokalemia, hypomagnesemia, hypocalcemia), or family history of sudden unexplained death or long QT syndrome
- History or evidence of a medical condition or any clinically significant disorder, condition, or disease (e.g., psychiatric or other mental health disorder, renal failure, hypertension, liver disease, anemia) that is uncontrolled despite treatment or that is likely, in the opinion of the investigator, to require a change in therapy, pose a risk to patient safety, interfere with the conduct of the study, have an impact on the study results, or affect the patient's ability to participate in the study
- Planned surgical intervention during the course of the study
- Patient who is a member of the investigational team or his/her immediate family

4.2 METHOD OF TREATMENT ASSIGNMENT AND BLINDING

Patients who meet all eligibility criteria will be randomized to one of the two treatment groups through the web-based response system (IxRS) on the first day of dosing. Patients will be randomized in a 1:1 ratio to receive 490 mg SC MSTT1041A Q4W or placebo, and stratified by baseline disease severity IGA score (IGA=3 vs. IGA=4) and region.

Study site personnel and patients will be blinded to treatment assignment during the study. The Sponsor and its agents will also be blinded to treatment assignment, with the exception of IxRS provider and prespecified personnel (e.g., IMC members).

While PK and ADA samples must be collected from patients assigned to the placebo arm to maintain the blinding of treatment assignment, PK and ADA assay results for these patients are generally not needed for the safe conduct or proper interpretation of this study. Laboratories responsible for performing study drug PK and ADA assays will be unblinded to patients' treatment assignments to identify appropriate samples to be analyzed. PK samples from patients assigned to the placebo arm will not be analyzed for study drug PK concentration except by request (e.g., to evaluate a possible error in dosing). Baseline ADA samples will be analyzed for all patients. Postbaseline ADA samples from patients assigned to the placebo arm will not be analyzed for ADAs except by request.

If unblinding is necessary for a medical emergency (e.g., in the case of a serious adverse event for which patient management might be affected by knowledge of treatment assignment), the investigator will be able to break the treatment code by contacting the IxRS. The investigator is not required to contact the Medical Monitor prior to breaking the treatment code; however, the treatment code should not be broken except in emergency situations.

If the investigator wishes to know the identity of the study drug for any reason other than a medical emergency, he or she should contact the Medical Monitor directly.

As per health authority reporting requirements, the Sponsor's Drug Safety representative will break the treatment code for all serious, unexpected suspected adverse reactions (see Section 5.7) that are considered by the investigator or Sponsor to be related to study drug. The patient may continue to receive treatment, and the investigator, patient, and Sponsor personnel, with the exception of the Drug Safety representative and personnel who must have access to patient treatment assignments to fulfill their roles (as defined above), will remain blinded to treatment assignment.

4.3 STUDY TREATMENT AND OTHER TREATMENTS RELEVANT TO THE STUDY DESIGN

The investigational medicinal products (IMPs) for this study are MSTT1041A and matching placebo.

MSTT1041A—Genentech, Inc.
33/Protocol GS40965, Version 1

4.3.1 Study Treatment Formulation, Packaging, and Handling

4.3.1.1 MSTT1041A and Placebo

MSTT1041A or matching placebo will be supplied by the Sponsor as sterile, clear, and colorless to slightly yellow liquid in glass vials. For information on the formulation and handling of MSTT1041A, see the pharmacy manual and the MSTT1041A Investigator's Brochure.

4.3.2 Study Treatment Dosage, Administration, and Compliance

The treatment regimens are summarized in Section [3.1](#).

No dose modifications should be performed in this study. Any dose modification should be noted on the Study Drug Administration electronic Case Report Form (eCRF). Cases of accidental overdose or medication error, along with any associated adverse events, should be reported as described in Section [5.4.4](#).

Guidelines for treatment interruption or discontinuation for patients who experience adverse events are provided in Section [5.1.2.1](#).

4.3.2.1 MSTT1041A and Placebo

Patients who meet eligibility criteria during the screening period will be randomly allocated to receive treatment with MSTT1041A 490 mg SC Q4W or placebo.

Additionally, patients in the active treatment arm will receive a loading dose of 245 mg SC MSTT1041A at the Week 1 visit; patients in the placebo arm will receive placebo (see [Appendix 1](#)).

Study drug administration must occur after all other procedures have been completed at each office visit, unless specifically indicated otherwise. Study drug will be administered at the study site by trained medical personnel. Except for the loading dose, each dose of study drug (MSTT1041A or placebo) will be administered as four SC injections (for a total of 7 mL), one in each quadrant of the abdomen. The loading dose (MSTT1041A or placebo) will be administered as two SC injections (for a total of 3.5 mL). See the pharmacy manual for details on study drug preparation and administration.

All patients will be observed for at least 30 minutes after each dose and longer in the event of an injection-site reaction, approximately 60 minutes, as determined by the investigator. If a patient develops any signs or symptoms to suggest a systemic hypersensitivity reaction or anaphylactic event, longer observation may be warranted in the opinion of the investigator.

Patients who are unable to tolerate study drug will discontinue treatment but will be asked to continue with study assessments. Study drug may be resumed after the events resolve, if the investigator determines that the event was not related to study drug and the investigator and Medical Monitor agree that it is appropriate for the patient to resume

study drug. See Section 5.1.2 for specific guidelines for withholding or discontinuing study drug for patients who experience adverse events.

4.3.3 Background Treatment

All patients are required to apply moisturizers (emollients) at least twice daily for at least the 7 consecutive days immediately before the randomization visit and to continue throughout the study (all 24 weeks where applicable). However, to allow adequate assessment of skin dryness, moisturizers should not be applied on the area(s) of non-lesional skin designated for such assessments for at least 8 hours before each office visit. All types of moisturizers are permitted, but patients may not initiate treatment with prescription moisturizers or moisturizers containing additives such as ceramide, hyaluronic acid, urea, or filaggrin degradation products within 1 week before the randomization visit or after enrollment into the double-blind treatment period.

If prescription moisturizers containing these additives are initiated more than 1 week before the randomization visit, they are permitted. Patients should continue using stable doses of permitted moisturizers throughout the study.

4.3.4 Rescue Treatment

If medically necessary (i.e., to control intolerable AD symptoms), rescue treatment for AD may be provided to patients at the discretion of the investigator. For the purpose of efficacy analysis, patients who receive rescue treatment during the study treatment period will be considered treatment failures, but they will continue study treatment if rescue consisted of topical medications (e.g., TCS). TCI may be used for rescue, but it should be reserved for problem areas only (e.g., face, neck, intertriginous, and genital areas, etc.). If possible, investigators should attempt to limit the first step of rescue therapy to topical medications and escalate to systemic medications only for patients who do not respond adequately after at least 7 days of topical treatment. If a patient receives rescue treatment with systemic corticosteroids or nonsteroidal systemic immunosuppressive drugs (e.g., cyclosporine, methotrexate, mycophenolate-mofetil, azathioprine), study treatment will be discontinued.

After systemic treatment with these medications is completed, study treatment may be resumed if deemed appropriate by the investigator and the Medical Monitor, but not sooner than 5 half-lives after the last dose of systemic rescue medication.

All patients will complete all study visits and assessments regardless of completion of study treatment and regardless of receipt of rescue treatment for AD. Investigators should make every attempt to conduct efficacy and safety assessments (e.g., disease severity scores, safety labs) immediately before administering any rescue treatment. An unscheduled visit may be used for this purpose if necessary.

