6.4 EFFICACY ANALYSES

Efficacy analyses will be based on the intent-to-treat (ITT) approach. All patients randomized (ITT population) will be included in the analysis, with patients grouped according to the treatment assigned at randomization. Hypothesis testing for the efficacy endpoints will be performed for each MSTT1041A dose level and the placebo group.

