6.4.1 Primary Efficacy Endpoint

The primary efficacy endpoint for this study is percent change from baseline to Week 16 of total EASI score. A mixed-effect model for repeated measures (MMRM) model will be used, with percent change (post baseline change divided by baseline value) as the dependent variable. The model will include baseline value of the EASI score, treatment arms, visits, treatment arm by visit interaction, and stratification factors as listed in Section 3.1. To account for repeated observations with patients, a random patient effect will be added to the model. The MMRM model will provide adjusted least-square means of percent change from baseline at Week 16 for each of the treatment arms with the corresponding standard error, 95% CI and p-values.

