6.4.2 Secondary Efficacy Endpoints

All secondary endpoints involving binary outcome measures will be analyzed using the Cochran-Mantel-Haenszel chi-square test. Patients with missing results at Week 16 will be considered non-responders for the corresponding endpoint.

Percent and absolute change from baseline for (approximately) continuous endpoints will be analyzed using a MMRM model as described for primary endpoint in Section 6.4.1. The MMRM model will provide adjusted least-square means of percent change from baseline at Week 16 for each of the treatment arms with the corresponding standard error, 95% CI and p-values.

Summary statistics of the (approximately) continuous endpoints will be calculated for each treatment arm in absolute changes and raw values. Mean, standard deviations, medians, and lower and upper quartiles, as well as minimum and maximum will be reported. For all summaries involving change from baseline, patients without baseline values will be excluded from the analyses.

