Appendix 1: Schedule of Activities

- ^a If a patient is unable to complete all study visits and assessments, the patient should be asked to return to the clinic for an early termination visit. This visit should occur approximately 4 weeks after the final dose of study drug (see Section 4.6.2).
- ^b Any of the study procedures noted may be performed at an unscheduled visit, but not all are required.
- ^c Informed consent must be documented before any study-specific screening procedure is performed.
- ^d Includes evaluation of the head, eyes, ears, nose, and throat, and the cardiovascular, dermatologic, musculoskeletal, respiratory, gastrointestinal, and neurologic systems. Record abnormalities observed at baseline on the General Medical History and Baseline Conditions eCRF. At subsequent visits, record new or worsened clinically significant abnormalities on the Adverse Event eCRF.
- ^e Perform a limited, symptom-directed examination at specified timepoints and as clinically indicated. Record new or worsened clinically significant abnormalities on the Adverse Event eCRF.
- ^f Questionnaires (██████████, pruritus and sleep NRS) will be self- or interviewer-administered before the patient receives any information on disease status, prior to the performance of non-PRO assessments, and prior to the administration of study treatment.
- ^g Assessment will be conducted only during an office visit (i.e., not at a telephone visit).
- ^h Will only be conducted at a telephone visit. For the Week 2 visit, if the patient does not have an office visit (chooses a telephone visit), collect pruritus and sleep NRS.
- ⁱ Includes respiratory rate, pulse rate, and systolic and diastolic blood pressure, ideally while the patient is in a seated position, and temperature. Record abnormalities observed at baseline on the appropriate eCRF. At subsequent visits, record new or worsened clinically significant abnormalities on the Adverse Event eCRF.
- ^j All women of childbearing potential will have a serum pregnancy test at screening. Urine pregnancy tests will be performed at specified subsequent visits. If a urine pregnancy test result is positive, it must be reported immediately, and study drug will not be administered that day. The positive urine pregnancy result must be confirmed by a serum pregnancy test. Refer to Section 5.4.3.1 for management of a patient with a positive pregnancy test.

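### Rescued patients are treatment failures under Section 4.3.4, but the primary MMRM in Section 6.4.1 uses their scores after rescue with no exception

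*Combined protocol and SAP*

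**What the plan says.** Section 4.3.4 contains an analysis rule as well as clinical instructions: "For the purpose of efficacy analysis, patients who receive rescue treatment during the study treatment period will be considered treatment failures". Study drug continues after topical rescue, and follow-up does not stop: "All patients will complete all study visits and assessments regardless of completion of study treatment and regardless of receipt of rescue treatment for AD". The section also asks for a measurement just before rescue ("Investigators should make every attempt to conduct efficacy and safety assessments") and adds: "An unscheduled visit may be used for this purpose if necessary".

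Section 6.4.1 defines the primary analysis as an MMRM "with percent change (post baseline change divided by baseline value) as the dependent variable". Its terms are baseline EASI, arm, visit, arm by visit and the stratification factors, with a random patient effect. On the population, Section 6.4 says: "All patients randomized (ITT population) will be included in the analysis". Section 6.4.2 extends the model: "Percent and absolute change from baseline for (approximately) continuous endpoints will be analyzed using a MMRM model". The synopsis repeats the primary model.

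The visible text of Section 6 does not mention rescue. Treatment failure appears there once, in 6.2, as something to list and summarize. Section 6.9 leaves the details of sensitivity analyses to a Data Analysis Plan that is not among the documents.

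**The concern.** The protocol announces a rule for efficacy analysis, and the primary model has no step that applies it. A patient who uses a topical corticosteroid at Week 10 and improves by Week 16 is a failure under 4.3.4. In the model of 6.4.1 that patient contributes the improved Week 16 score to the assigned arm.

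An analyst who notices this has at least three options: use the score as observed, set it to missing, or replace it with a failure value. These answer different questions and can give different estimates. With the choice unmade, two analysts who both follow the protocol could report different primary results. A rule chosen after treatment codes are known would be open to challenge.

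**Working it through.** **Inputs from Section 6.1.** About 90 patients, 1:1, so 45 per arm; 25% dropout; difference 34 points; SD 40.6, stated for placebo; two-sided 0.05. Assumption: the same SD applies in the active arm.

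**The plan's own figure.** Evaluable per arm: 45 × 0.75 = 33.75, taken as 34. Standard error: 40.6 × √(2/34) = 9.85. Noncentrality: 34 / 9.85 = 3.45. Power from the noncentral t (66 df) is 92.5%, or 91.8% with 33 per arm. The plan's claim of at least 80% is reproduced.

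**Scores on rescue used as observed.** The documents give no rescue rates (r) or points gained on rescue (g), so every value below is an assumption. A rescued patient's percent change improves by g, so

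difference = 34 − (r_placebo − r_active) × g.

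With SD held at 40.6 and 34 per arm:

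| Rescue, placebo / active | Gain | Difference | Power |
|---|---|---|---|
| 30% / 10% | 15 | 34 − 0.20 × 15 = 31.0 | 87.3% |
| 30% / 10% | 30 | 34 − 0.20 × 30 = 28.0 | 80.0% |
| 30% / 10% | 45 | 34 − 0.20 × 45 = 25.0 | 70.6% |
| 10% / 30% | 30 | 34 + 0.20 × 30 = 40.0 | 97.9% |

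The difference that gives exactly 80% power is 28.00 at 34 per arm and 28.43 at 33. Power therefore falls below 80% only if rate gap × gain exceeds 34 − 28.00 = 6.0 points (5.6 at 33 per arm).

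Rescue also changes the spread. If it is unrelated to score, each arm's variance rises by r(1 − r)g². For 30%/10% and g = 30 the variances are 1648.4 + 189 = 1837.4 and 1648.4 + 81 = 1729.4. The pooled SD is 42.2 and power is 77%. If the worst scorers are the ones rescued, the gain narrows the spread and power at 28.0 is above 80%.

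**What a failure value could cost.** One possible value was examined: the worse of 0% change and the last value before rescue. Assumptions: Week 8 and Week 16 percent change bivariate normal, SD 40.6, correlation 0.7; Week 16 means −25 (placebo) and −59 (active); Week 8 means equal to these or 75% of them; rescue just after Week 8.

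For rescue unrelated to score with equal means at both visits, a rescued patient's expected value is E[max(0, X)]: 6.7 for placebo and 1.3 for active. At 20%/20% the difference is 0.8 × 34 + 0.2 × (6.7 − 1.3) = 28.3.

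| Rescue, placebo / active | Worst scorers rescued | Unrelated to score |
|---|---|---|
| 30% / 10% | 36.1–36.5, power 91–93% | about 37–38, power 96–97% |
| 20% / 20% | 32.0–32.2, power 81–85% | about 28.3, power about 79% |
| 10% / 30% | 26.1–27.0, power 63–69% | about 19, power about 44–45% |

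For comparison, as-observed handling at 20%/20%, unrelated to score, with a 30-point gain leaves the difference at 34 with power of about 90%.

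Limits: one rescue time, a normal model that allows changes below −100%, a t-test in place of the MMRM, and dropout only through the sample size.

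**The case against.** The best defence is that failure is responder language. Section 4.5.9.3 dichotomizes the IGA into success or failure, and 6.2 treats failure as an item to summarize. On that reading the intent-to-treat statement and full follow-up after rescue would support using continuous scores as collected. Part of this stands: because failure has no value on the percent-change scale, 4.3.4 is incomplete there, and its wording alone does not tell an analyst what to enter. The reading still does not remove the problem. The sentence in 4.3.4 covers efficacy analysis without limiting itself to responders, and the intent-to-treat statement fixes which patients are analysed and in which arm, not which of their values are used.

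A second defence is that the Data Analysis Plan may contain a rule. It may, but 6.9 refers to it only for sensitivity analyses, so it cannot be assumed to settle the primary one. The contents list also shows a redacted entry after 6.4.2. The claim is therefore limited to the visible text.

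A reader might infer that the responder endpoints share the gap. They do not: failure translates directly to non-response, and 4.3.4 already binds. A reader might also infer that the documents dictate a particular failure value, such as 0% change. They do not.

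**Conclusion.** The point holds. As written, the primary MMRM and the continuous secondary MMRMs use scores obtained on rescue as the effect of the assigned arm, which does not carry out 4.3.4. The bias is toward no difference if placebo patients are rescued more often, and away from it if active patients are.

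The size is unknown because the documents give neither a rescue rate nor a rescue effect. The move from 34 to 28 points is an illustration. It also assumes that the 34 points in 6.1 exclude scores on rescue, which 6.1 does not say; if they are already included, the shift does not apply.

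A reader might infer that the trial is underpowered. The documents do not support that: the stated power is reproduced with room to spare, and falling below 80% takes a particular combination of assumed rates and gain. The reason to act is that the primary analysis lacks a step its own protocol calls for, whatever the illustrations show.

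**What to change.** Before unblinding, and so before the Week 16 analysis described at the start of Section 6, amend 6.4.1, and through it the continuous endpoints in 6.4.2. State that values after first rescue in the treatment period are not used as observed in the primary MMRM. Name one primary handling:

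- **A defined failure value**, for example one based on the pre-rescue assessment requested in 4.3.4. It must be defined for both percent and absolute change. It also needs a fallback, such as the last earlier scheduled value, because footnote b of Appendix 1 says of unscheduled visits: "Any of the study procedures noted may be performed at an unscheduled visit, but not all are required".
- **Values after rescue set to missing.**

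Report the other handling and the as-observed MMRM as named sensitivity analyses. Align the synopsis.

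The cost is a few sentences and two extra runs on data already being collected. Each option has a price. A failure value relies on imputation and can lower power, as the second table shows. Setting values to missing relies on a missing-at-random assumption and gives no penalty for failure, so it stops crediting rescue without scoring it as failure. The clinical rescue rules do not change.
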